3.1.5 Duration of Patient Participation

It is estimated that the total duration of the patient participation in the current study will not exceed 67 days.

Stage I: The duration of the patient participation in the Stage I of the study will not exceed 33 days, including a maximum of 3 days of screening period, a treatment period of 10 consecutive days and a study data collection period of 28 (+2) days.

Study treatments Favipiravir/Placebo will be administered over 10 consecutive days. If the patient is discharged before Day 10, the patient will be required to continue the remainder of the treatment course at home. However, the above-mentioned treatment period will be shortened if it is necessary to discontinue administration of the study drug due to AEs or other circumstances.

The patients will be discharged when the Principal Investigator or a medically qualified Sub Investigator judges that the patient is fit for discharge.

Day 10 will be considered as the EOT assessment.

1. If the patient remains in the hospital until Day 10, the EOT will be performed at the site and all the scheduled assessments for Day 10 will be performed (details mentioned in [Section 6.3.1.3](#)).
2. If the patient is discharged before Day 10, the EOT can be performed either as an onsite visit or will be performed at the patient's home (details mentioned in [Section 6.3.1.4](#)).
 - c. On-site visit: If the patient is able to visit the hospital on Day 10, procedures for an unscheduled visit will be performed.

OR

- d. At home: If the patient is unable to visit the hospital for the EOT, study nurse or phlebotomist will visit the patient at his/her residence to collect blood sample for safety assessments. A nasopharyngeal swab or oropharyngeal swab will be collected from the patient and sent for detection (qualitative) of SARS-CoV-2 RNA by RT-PCR assay based on Investigator's discretion for individual patients. A telephonic follow up will be performed to enquire on treatment emergent AEs experienced, concomitant medication and COVID-19 associated symptom for assessment of clinical relapse.

Day 28 will be considered the end of study visit.

If patient is discharged from the hospital before Day 28, the assessments mentioned in the end of study visit (Day 28) will be performed before the patient is discharged. After discharge, telephonic follow up will be performed on Day 10 (applicable only for patients who are discharged earlier than Day 10 and if patients are unable to visit the site for EOT on Day 10), Day 14, Day 21 and Day 28. The telephonic follow up will be as applicable for the individual patient, depending upon the actual day when (s)he is discharged. A 2-day window period is allowed for telephonic follow up.

In case the patient remains admitted in the hospital beyond Study Day 28, the end of study assessments will be performed for the patient on Day 28 (+2) days.

Study code: NV-05-983-2020
Protocol No.: CVD-04-CD-001
Sponsor name: [name], Limited
Clinical Study Protocol

Stage II:

The duration of the patient participation in the Stage II of the study will not exceed 34 days. Two telephonic follow up assessments will be performed on Day 42 and Day 60. The patients will be followed up for AEs or for 'clinical relapse' of COVID 19. An additional visit to the hospital (for further assessment) may be scheduled for such patients, if required. A 2-day window period is allowed for telephonic follow up.

3.1.6 Completion or Discontinuation of the Clinical Study and Discontinuation of Administration of the Study Drug (Completion or Discontinuation by Individual Patient)

3.1.6.1 Study Discontinuation

3.1.6.1.1 Study discontinuation criteria

When a patient meets any of the following criteria, the Principal Investigator or a Sub-Investigator will discontinue the patient from the study.

- a. The patient requests withdrawal from the clinical study
- b. The patient died
- c. The patient is lost to follow-up
- d. The patient is otherwise deemed ineligible to continue in the study by the Principal Investigator or a Sub-Investigator (e.g adverse event or pregnancy)
- e. Upon request by the CRO or Sponsor Medical Monitor (with appropriate justification)

3.1.6.1.2 Study discontinuation procedures

If the patient is discontinued from the clinical study based on criteria mentioned in [Section 3.1.6.1.1](#), the Principal Investigator or a Sub-Investigator is to take appropriate action and conduct the assessments scheduled for Day 28 as specified in [Section 6.3.1.5](#) before the patient is discharged.

The date of discontinuation from the clinical study, the reason for discontinuing the patient from clinical study, and other details are to be investigated. One of applicable reason for discontinuation from the list below will be entered in the eCRF.

When the patient misses the scheduled visits, the Principal Investigator or a Sub-Investigator will confirm the patient's condition using methods such as telephone calls and mail and encourage the patient to visit the site. A follow-up investigation regarding the subsequent course of symptoms, and the presence or absence of AEs, will also be conducted within the scope of the patient's cooperation, and the results will be recorded. When a follow-up investigation is impossible (because of a change of residence or other factors), such situations will also be recorded. A patient will be called 'lost to follow-up' if there is no response from the patient even after 3 documented telephone contact attempts on 3 different days.

Study code: NV-05-983-2020
Protocol No.: CVD-04-CD-001
Sponsor name: [name], Limited
Clinical Study Protocol

3.1.6.2 Study Treatment Discontinuation

3.1.6.2.1 Study treatment discontinuation criteria

When a patient meets any of the following criteria, the Principal Investigator or a Sub-Investigator will discontinue administering the study drug to that patient.

- a. The patient requests withdrawal from the clinical study
- b. If the patient requests discontinuation of administration of the study drug
- c. The patient died
- d. The patient is lost to follow-up
- e. If an AE occurs and the Principal Investigator or a medically qualified Sub-Investigator judges that continuing with the administration of the study drug would not be in the interest of patient's safety or well-being
- f. If a patient experiences a serious adverse event assessed by Investigator and/or Medical Monitor to be reasonably causally related to the IMP (FPV/Placebo)
- g. If a patient becomes pregnant while receiving IMP (FPV/Placebo)
- h. If patient's serum uric acid or hepatic transaminases levels are assessed as Grade 3 severity by National Institutes of Health (NIH) National Cancer Institute (NCI) Common Terminology Criteria for Adverse Events (CTCAE)²³, at any timepoint during the treatment period
- i. If a patient is otherwise deemed ineligible to continue in the study by the Principal Investigator or a Sub-Investigator
- j. Upon request by the CRO or Sponsor Medical Monitor (with appropriate justification)

3.1.6.2.2 Study treatment discontinuation procedures

If the study drug administration is discontinued based on [Section 3.1.6.2.1](#), the Principal Investigator or a Sub-Investigator need to take appropriate action. The date of, and reasons for, discontinuing administration of the study drug and the details (including actions taken after discontinuation of drug administration and the outcome, if the study drug was discontinued due to an AE) are to be investigated and captured in the eCRF. One of applicable reason for discontinuation from the list below will be entered in the eCRF.

Even if the administration of study treatment is stopped, patients will be encouraged to continue in the study and provide the applicable scheduled assessments, as specified in [Section 6.3](#) until the patients are discharged, as long as they do not meet the criteria for study discontinuation.

Study code: NV-05-983-2020
 Protocol No.: CVD-04-CD-001
 Sponsor name: [name], Limited
 Clinical Study Protocol

4 STUDY POPULATION

The study population will consist of patients of either sex, 21 to 80 years of age, who test positive for SARS-CoV-2 by RT-PCR assay using a respiratory tract sample (nasopharyngeal swab or oropharyngeal swab or nasal aspirate or tracheobronchial aspirate), have moderate to severe clinical presentations of COVID-19 and require hospitalization. An adequate number of patients will be screened to randomize 780 patients in a 1:1 ratio, so as to have approximately 390 patients in favipiravir + supportive care group and 390 patients in placebo + supportive care group.

4.1 Enrollment

Patients are eligible for enrolment into the study if they meet all the inclusion criteria and do not meet any of the exclusion criteria.

4.1.1 Inclusion Criteria

Patients must satisfy all the following criteria to be included in the study:

1. Male and female patients aged 21 to 80 years (both inclusive)
2. Patients who have tested positive for SARS-CoV-2 by RT-PCR assay using a respiratory tract sample (either nasopharyngeal swab OR oropharyngeal swab OR nasal aspirate OR tracheobronchial aspirate) collected within 72 hours prior to randomization
3. Patients should be hospitalized
4. Patients having moderate or severe COVID-19* with a score of > 4 on the 10-point ordinal scale of clinical status used by WHO in the SOLIDARITY trial, at baseline assessment [i.e., patients with blood oxygen saturation (SpO₂) <95% at rest on room air at sea level and requiring supplemental oxygen].

*Note: This includes patients clinically assigned as:

- I. 'moderate' COVID-19
 - a. symptoms which could include fever, cough, sore throat, malaise, headache, muscle pain, gastrointestinal symptoms or shortness of breath with exertion and/or clinical signs, such as respiratory rate ≥ 20 breaths per minute or heart rate ≥ 90 beats per minute
 - AND
 - b. blood oxygen saturation (SpO₂) of 94% at rest on room air at sea level
- II. 'severe' COVID-19
 - a. symptoms which could include any symptom of moderate illness or shortness of breath at rest, or respiratory distress and/or clinical signs, such as respiratory rate ≥ 30 per minute or heart rate ≥ 125 per minute
 - AND
 - b. blood oxygen saturation (SpO₂) $\leq 93\%$ on room air at sea level or PaO₂/FiO₂ <300*

Study code: NV-05-983-2020
 Protocol No.: CVD-04-CD-001
 Sponsor name: [name], Limited
 Clinical Study Protocol

The above-mentioned definitions of COVID-19 severity are adapted from the FDA Guidance document COVID-19: Developing Drugs and Biological Products for Treatment or Prevention - Guidance for Industry Final Document dated May 2020²⁴

5. Female patients of childbearing potential*

- a. must have a negative serum pregnancy test at screening
- b. should not be lactating; and not planning to become pregnant/breast feed during the treatment period and for 7 days after the last dose of study medication.
- c. should commit to the use of **TWO** forms of study-acceptable contraception methods, including a barrier method (eg. diaphragm) along with one or more of the following methods of contraception for the duration of the treatment period and for 7 days after the last dose of study medication:
 - i) hormonal methods [insertable, injectable, transdermal, or combination oral (estrogen+ progestin)] or
 - ii) intrauterine contraceptive device

*Note: Female patients who are sexually abstinent or whose male sexual partner has undergone vasectomy at least three months prior to the start of study treatment in the trial may be enrolled at the Investigator's discretion, provided that they are counseled to remain sexually inactive for the duration of the study and understand the possible risks involved in getting pregnant during the study. Patients must also agree to use **TWO** forms of study-acceptable contraception methods should they become sexually active during the treatment period and for 7 days after the last dose of study medication.*

*Note: A female patient is considered of childbearing potential unless she is:

- a. postmenopausal for at least 12 months prior to study product administration, or
 - b. without a uterus and/or both ovaries or has been surgically sterilized (ie, tubal ligation or has a fallopian tube blocking coil) for at least 6 months prior to study product administration.
6. Male patients should agree to abstain from sexual intercourse or to use double-barrier contraception (e.g. condom with spermicide) for the duration of the treatment period in the study and for at least 7 days after receiving the last dose of study medication. Male patients should also avoid semen donation or providing semen for *in-vitro* fertilization during the above-mentioned duration.
 7. Able and willing to provide informed consent
 8. Able to understand the trial requirements and comply with trial medications and assessments in the opinion of the Investigator
 9. Should not have received investigational treatment from participation in another clinical trial within 30 days prior to randomization in the current trial and agrees not to participate in other clinical studies during the entire study period

Study code: NV-05-983-2020
 Protocol No.: CVD-04-CD-001
 Sponsor name: [name], Limited
 Clinical Study Protocol

4.1.2 Exclusion Criteria

Patients who meet any of the following criteria will be disqualified from entering the study:

1. Critically ill patients, defined as those who are candidates for endotracheal intubation and mechanical ventilation, Extracorporeal Membrane Oxygenation (ECMO), or clinical diagnosis of respiratory failure (i.e., clinical need for one of the preceding therapies, but preceding therapies not able to be administered in setting of resource limitation) and those with shock (defined by systolic BP <90 mm Hg, or diastolic BP <60 mm Hg or requiring vasopressors) or multi-organ dysfunction/failure at baseline

Note: *The above-mentioned definition of 'critically ill' COVID-19 patients is as defined in the FDA Guidance document COVID-19: Developing Drugs and Biological Products for Treatment or Prevention - Guidance for Industry Final Document dated May 2020²⁴*

2. Patients in whom the first onset of symptoms/signs suggestive of COVID-19 illness was observed >10 days earlier to the baseline assessment and randomization
3. Patients who have used interferon beta 1-a (IFN- β -1a) preparations or drugs with reported anti-viral action against SARS-CoV-2 (hydroxychloroquine sulfate, chloroquine phosphate, lopinavir-ritonavir combination drugs, ciclesonide, nafamostat mesylate, camostat mesylate) within 9 days after development of fever ($\geq 37.5^{\circ}\text{C}$)

Note: The above-mentioned exclusion criterion is not applicable in case of patients with history of human immunodeficiency virus infection or infective hepatitis in whom use of anti-viral drugs or interferons are prescribed for treatment of the underlying condition and who are currently receiving one or more of these medications (as maintenance treatment) at the time of randomization. The infection episode in question is a relapse of, or reinfection with SARS-CoV-2

4. Patients suspected to have a complication of congestive cardiac failure based on Investigator's clinical judgement
5. Patients with moderate and severe hepatic dysfunction equivalent to Grade B and Grade C in the Child-Pugh classification respectively
6. Patients with ALT and AST levels > 5 times upper limit of normal (ULN) at screening evaluation
7. Patients with renal impairment requiring dialysis
8. Patients with serum uric acid higher than the ULN at screening evaluation
9. Patients with history of hereditary xanthinuria
10. Patients who have been diagnosed with xanthine urinary calculus
11. Patients with a history of gout or patients who are currently being treated for gout
12. Patients who are taking immunosuppressants
13. Patients who were administered Favipiravir in the past 30 days
14. Patients with known hypersensitivity reaction to Favipiravir

Study code: NV-05-983-2020
Protocol No.: CVD-04-CD-001
Sponsor name: [name], Limited
Clinical Study Protocol

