The main transmission routes for SARS-CoV-2 are respiratory droplets and close contact such as touching an infected person or the surfaces and fomites that the infected person has either touched, or on which large virus-containing droplets expired by the infected person have landed.⁷

SARS-CoV-2, a single-stranded positive sense RNA virus, targets cells through the viral structural spike (S) protein embedded in the viral membrane (M) that binds to the angiotensin-converting enzyme 2 receptor on target host cells. Following receptor binding, the virus particle uses host cell receptors and endosomes to enter cells. Once inside the cell, viral polyproteins are synthesized that encode for the replicase-transcriptase complex. The virus then synthesizes ribonucleic acid (RNA) via its RNA-dependent RNA polymerase (RdRp). Structural proteins are synthesized leading to completion of assembly and release of viral particles.⁸

Study code: NV-05-983-2020
Protocol No.: CVD-04-CD-001
Sponsor name: [name], Limited
Clinical Study Protocol

Within six days of the onset of symptoms, patients with COVID-19 infections demonstrate high viral loads in their upper and lower respiratory tract. A nasopharyngeal swab and/or an oropharyngeal swab are often recommended for screening or diagnosis of early infection. For late detection and monitoring of patients with severe COVID-19 pneumonia, sputum or bronchoalveolar lavage should be used for collecting lower respiratory tract specimens.⁹

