5.1.1 Method of Assigning Patients to Treatments

A total of 780 eligible patients will be assigned randomly to one of two treatment groups in 1:1 ratio, so as to have approximately 390 patients in favipiravir + supportive care group and 390 patients in placebo + supportive care group. Details of the interim analysis and futility assessment are provided in the Statistical Analysis Plan (SAP) for the Interim Analysis.

Patients will be randomized to the favipiravir + supportive care group or placebo + supportive care group in a 1:1 ratio and a conditional stratification will be performed to include at least 15% of female patients, at least 30% of patients with either category of baseline disease severity (i.e., moderate and severe) and at least 30% of patients aged more than 50 years randomized in each of the treatment groups. If there is an impact on the patient recruitment rate due to limits enforced by the stratification of patients based on the category of baseline disease severity, a decision may be made to waive the stratification based on disease severity. The percentage of stratification may be adjusted according to the re-estimated sample size. The randomization schedule will be generated by CRO statistical team, in SAS, (version 9.4 or higher), according to CRO's standard operating procedures (SOPs).

All patients who sign an IRB/IEC approved informed consent form and authorization for the use and disclosure of protected health information will be assigned a unique patient identity code (PIC) consisting of 03-digit center/site code and three digits (004) patient specific code. The randomization code will be captured separately as an additional identity.

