11.4 Efficacy Analyses

11.4.1 Primary Efficacy Analyses

Analysis of the primary endpoint:

The time from the start of administration of the study drug to time to *resolution of hypoxia* as described in the [Section 3.1.3.1.1](#) will be compared between the treatment groups using the Cox proportional hazard model with age, gender and disease severity (moderate and severe) as factors and baseline WHO ordinal score at the start of administration of the study drug as baseline covariates. The hazard ratio and its corresponding 95% confidence interval (CI) and p-value will be obtained from the above Cox proportional hazard model; Also Median time, Inter quartile range estimate etc. will be presented and Kaplan-Meier plot will be plotted. All the efficacy analysis mentioned will be performed using ITT and PP population.

For censored patients who died of any cause, discontinued or were lost to follow-up due to treatment-related adverse events or lack of efficacy, they will be censored at Day 28. However, censored patients who discontinued or were lost to follow-up for reasons that were independent of the study medication will be censored at the day of discontinuation of lost to follow-up. Censored patients who were still in the study follow-up at the time of the analysis will be censored at the last day of available follow-up data.

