10.2 Demographic Data and Baseline Characteristics

The demographic data and baseline characteristics will be summarized using descriptive statistics or by frequency and percentage for the applicable parameters using SAF Population by treatment group.

- Gender
- Age
- Race
- Height
- Weight
- Nationality
- BMI
- No. of days since first onset of symptoms associated with COVID-19 (at baseline)
- Clinical Status by 10-point ordinal scale
- Clinical Status by 8-point ordinal scale
- National Early Warning Score (NEWS Score)
- COVID-19 associated symptoms
- RT-PCR (Was RT-PCR test performed for SARS-CoV 2 ?)
- RT-PCR result
- Chest X-ray total RALE score

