10.6 Efficacy Analysis

10.6.1 Primary Efficacy endpoint

Primary Efficacy endpoint will be as follows:

1. Time to resolution of hypoxia

The primary efficacy endpoint is “Time to resolution of hypoxia (Time frame: Up to 28 days)”

This endpoint will be considered to have been met when the patient has attained a score of 4 or lower on the 10-point ordinal scale of clinical status and either of a) or b), (as applicable) and c) is met:

- a) Score is ≤ 4 on consecutive assessments over the next 5 days, if patient continues to remain in hospital (i.e., has not been discharged).

OR

Statistical Analysis Plan
Sponsor: [name], Inc

Study Number: NV-05-983-2020

Version: 2.0 Date: 06JAN2021

- b) Patient was discharged before five consecutive assessments (after reaching a score of 4)

AND

- c) The patient has survived and has not been re-admitted to hospital for COVID-19 management through Day 28.

*Note: Part c) is applicable to patients in both a) and b).
 i.e. Time to resolution of Hypoxia = either "a and c" OR "b and c" is met.*

Time to resolution of hypoxia will be compared between the treatment groups using the Cox proportional hazard model with age, gender, and baseline score on the 10-point ordinal scale of clinical status as covariates. The hazard ratio and its corresponding two-sided 95% confidence interval (CI) and two-sided p -value at 5% level of significance will be obtained from the above Cox proportional hazard model.

As the patients were in the hospital until discharge, missing data in the daily WHO clinical status score were few. To facilitate the definition of the durable response, a very limited and conservative imputation will be implemented to impute a missing clinical status score if adjacent to a valid score on both sides, the imputed score will be the higher (worse) of the two, as discussed in Section 9.5.1.

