10.7.10 Hospitalization

Listing of patients who require oxygen supplementation, ICU admission, Oxygen by HFNC or NIV and Invasive Mechanical Ventilation will be listed.

10.7.11 Subgroup Analysis:

Subgroup analysis will be performed for the “Time to resolution of hypoxia” by considering the severity category (moderate vs severe categories) as a subgroup using ITT population as an observed case analysis.

Subgroup analysis will be performed for the “Time to resolution of hypoxia” by considering the race category (White/ Caucasian vs Non-White / Non-Caucasian) as a subgroup using ITT population as an observed case analysis.

Subgroup analysis will be performed for the “Time to resolution of hypoxia” by considering the age category (Age group <50 years, Age group ≥50 years) as a subgroup using ITT population as an observed case analysis.

Subgroup analysis will be performed for the “Time to resolution of hypoxia” by considering the gender category as a subgroup using ITT population as an observed case analysis.

11 Deviation from the Study Protocol

Not applicable

12 Database Lock and Unblinding

There will be two database lock for this study. One for stage I (Primary) and another one for Stage II (Secondary) analysis. The SAP will be finalized prior to primary database lock. After the data cleaning process is finalized according to the data management plan (DMP) and the assignment of patients to the analysis populations is agreed and signed by the Sponsor, the study database will be locked for primary and secondary separately.

13 References

1. Lachin J. M. (1999). *Worst-Rank Score Analysis with Informatively Missing Observations in Clinical Trials. Controlled Clinical Trials. 20:408–422.*

	Statistical Analysis Plan Sponsor: [name], Inc	
	Study Number: NV-05-983-2020	Version: 2.0 Date: 06JAN2021

14 Appendices

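### Days since symptom onset is a listed baseline variable in an antiviral trial that admits patients 0 to 10 days into illness, but no planned model or subgroup uses it; adding it is nearly free and could recover up to about 10 points of power

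*Protocol*

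**What the plan says.** Protocol 4.1.2, exclusion 2, removes patients in whom "illness was observed >10 days earlier to the baseline assessment and randomization". There is no lower limit.

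SAP 10.2 lists "No. of days since first onset of symptoms associated with COVID-19 (at baseline" among the baseline characteristics, summarised by arm in the safety population. That is its only use:

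- **Primary model, SAP 10.6.1:** Cox model "with age, gender, and baseline score on the 10-point ordinal scale of clinical status as covariates". Protocol 11.4.1 has "age, gender and disease severity (moderate and severe) as factors and baseline WHO ordinal score".
- **Interim model, SAP Appendix I:** the same three covariates as SAP 10.6.1.
- **Sensitivity analyses, SAP 10.6.1:** a two-day definition of resolution, a log-rank test and a worst-rank test. None uses duration.
- **Secondary models, SAP 10.6.2:** the covariates named are a baseline symptom score, a baseline cycle-threshold value or a baseline ordinal score.
- **Randomisation, Protocol 5.1.1:** minimum shares of "at least 15% of female patients, at least 30% of patients with either category of baseline disease severity", and of patients over 50.
- **Subgroups, SAP 10.7.11:** severity, race, age and gender.

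Protocol 11.4.3 says exploratory analyses may be planned. The FDA guidance in Protocol Appendix I asks sponsors to consider adjusting for pre-specified prognostic baseline covariates.

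**The concern.** Favipiravir is justified in the protocol as an inhibitor of viral RNA polymerase, so how far the illness has run at first dose is a natural candidate both as a prognostic factor and as a modifier of effect. Two things are at stake.

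First, the hazard ratio is non-collapsible. Leaving out a covariate that predicts the outcome pulls the estimated treatment hazard ratio towards 1 and lowers power, even when the arms are balanced on it.

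Second, if benefit were concentrated in patients treated early, the overall result would be diluted, and the plan contains no pre-specified estimate that would show the pattern.

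**Working it through.** **1. The plan's own figures** (Protocol 11.10; two-sided test from SAP 10.6.1). Inputs: hazard ratio (HR) 1.25, alpha 0.05, power 80%, event probabilities 0.9 and 0.8 (mean 0.85), dropout 5%.

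- Events (Schoenfeld): 4(1.960 + 0.842)² / (ln 1.25)² = 31.40 / 0.0498 ≈ 631, as stated.
- Patients: 631 / 0.85 = 742, or 371 per arm, as stated.
- Randomised: 371 / 0.95 = 391 against 390 stated (371 × 1.05 = 390), an immaterial difference.
- Power: Φ(½√631 × ln 1.25 − 1.960) = Φ(0.843) = 80.0%.

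**2. Cost of leaving duration out of the Cox model.** Simulation of 742 patients, 1,500 runs per row. Control hazard is −ln(0.2)/28 = 0.0575 per day (80% events by Day 28), true HR 1.25, censoring at Day 28. Two inputs are assumptions: duration uniform over 0 to 10 days (SD √10 = 3.16 days), and its prognostic strength. With no prognostic effect the set-up gives about 371 × (0.800 + 1 − 0.2^1.25) = 371 × 1.666 = 618 events, so the reference power is 79% rather than 80%.

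| Assumed log-HR per SD | Hazard change per day | HR without / with duration | SE without / with | Power without / with | Gain (points) |
|---|---|---|---|---|---|
| 0 | 0% | 1.250 / 1.250 | 0.0806 / 0.0807 | 79.1 / 78.8% | −0.3 |
| 0.1 | 3.2% | 1.248 / 1.250 | 0.0807 / 0.0808 | 77.4 / 78.1% | 0.7 |
| 0.2 | 6.5% | 1.238 / 1.245 | 0.0809 / 0.0810 | 75.0 / 77.5% | 2.5 |
| 0.3 | 10% | 1.238 / 1.253 | 0.0811 / 0.0813 | 73.9 / 78.8% | 4.9 |
| 0.5 | 17% | 1.210 / 1.249 | 0.0819 / 0.0821 | 66.3 / 76.8% | 10.5 |

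The bottom row is a strong assumption: across the full window the hazard would change by a factor of exp(0.5 × 10 / 3.16) = 4.9. At 10% per day the factor is exp(0.3 × 10 / 3.16) = 2.6.

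These fits contain only treatment and duration. A separate 600-run check with an assumed binary severity covariate already in the model gave gains of 0.5 points at 5% per day and 3.7 points at 10% per day, with the SE again unchanged (0.0816 against 0.0817, and 0.0817 against 0.0819). Over 5% to 10% per day the gain is therefore small, from near 0 to about 5 points.

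**3. Effect confined to early treatment.** Let early-treated patients supply a share f of the 631 events with HR 1.25, and the rest have HR 1.

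- Overall HR ≈ 1.25^f. Overall power = Φ(½√631 × f × ln 1.25 − 1.960).
- f = 0.5: HR 1.12; Φ(1.401 − 1.960) = 29%.
- f = 0.6: HR 1.14; Φ(1.682 − 1.960) = 39%. A 300-run simulation with benefit up to Day 6 of a uniform Day 1 to 10 window gave HR 1.14 and 35% (Monte Carlo SE √(0.35 × 0.65 / 300) = 2.8 points).

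**4. What a duration analysis could detect.** Interaction power = Φ(ln 1.25 / √(4/(631f) + 4/(631(1 − f))) − 1.960). Early-subgroup power uses 631f events.

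| f | Early HR | Overall power | Early-subgroup power | Interaction power |
|---|---|---|---|---|
| 0.25 | 1.25 | 10% | 29% | 23% |
| 0.50 | 1.25 | 29% | 51% | 29% |
| 0.60 | 1.25 | 39% | 58% | 28% |
| 0.75 | 1.25 | 56% | 68% | 23% |
| 0.50 | 1.50 | 72% | 95% | 72% |

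**The case against.** The case against acting has several parts.

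- **The harm is assumed.** No passage says duration is prognostic for coming off oxygen, in which direction, or how strongly given age, gender and baseline score. All patients are hospitalised, on oxygen and RT-PCR positive within 72 hours of randomisation, so the spread of duration may be narrower than uniform. This stands, and it is why the size is given as a range starting at zero.
- **Loss of precision.** A reader might infer that adjustment would shrink the standard error. In a Cox model it does not; the SE stayed at about 0.08. The gain is less attenuation of the HR, and part of that shift is the difference between a marginal and a conditional HR.
- **A six-day treatment window.** The protocol's introduction says "Within six days of the onset of symptoms, patients with COVID-19 infections demonstrate high viral loads", and it is tempting to read that as a biological boundary for treatment. In context the sentence explains which specimen to take early and late. It sets no treatment window and cannot by itself justify a cut-point.
- **A hidden effect and an uninterpretable null.** The documents do not support this. The variable is tabulated, and Protocol 11.4.3 allows exploratory work, so the pattern could be examined afterwards. A duration interaction would itself usually miss an effect of HR 1.25. What is missing is pre-specification of one supportive estimate.
- **The plan already follows its guidance.** It adjusts for age and baseline score and has a severity subgroup, and the guidance only asks sponsors to consider adjustment. That is fair: omitting duration breaches nothing.
- **Complete recording is inferred.** The baseline-characteristics footnote to the assessment schedule does not list duration. Exclusion 2 and SAP 10.2 make collection very likely but do not prove that it is complete.

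What survives is that adjustment costs essentially nothing if duration is not prognostic (79% power either way).

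**Conclusion.** The point holds as a low-cost improvement, and the plan's design figures stand. Days since onset is a listed baseline variable that enters no model or subgroup. Omitting it costs about 0 to 10 points of power. The upper end needs a roughly fivefold hazard range across the window; the range is about 0 to 5 points at a 5% to 10% change in hazard per day. These figures rest on an assumed uniform spread of duration and an assumed prognostic strength that the documents do not supply.

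If benefit at HR 1.25 were confined to early-treated patients supplying half to 60% of events, the overall HR would be about 1.12 to 1.14 with power of about 29% to 39%, and no pre-specified analysis would describe it. That scenario is hypothetical. A duration analysis would describe the pattern with an interval but would not reliably confirm it, since interaction power is only about 23% to 29%.

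**What to change.** 1. In SAP 10.6.1, add days from first symptom onset to baseline, as a continuous covariate, to the primary Cox model. Make the change while blinded and before the Stage I database lock.
2. Make the same change to the interim model in SAP Appendix I and to Protocol 11.4.1, so that interim and final statistics come from one model. The SAP is dated 06JAN2021 and the interim covers the first 390 randomised or those enrolled by the end of 2020, whichever is earlier, so the interim may be imminent or already done. If it has been run unblinded, blinded staff should make the change, or the duration-adjusted model should be specified as a sensitivity analysis instead.
3. In SAP 10.7.11, add a treatment-by-duration estimate with a 95% confidence interval, preferably with duration continuous. A six-day split may be shown descriptively. Label it supportive, not confirmatory.
4. Check blind that the onset date is complete, and state how a missing value will be handled.

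The cost is a few sentences in three places. No patients or events are added, and no new data are needed if the onset date is complete. Adjusting for a pre-randomisation variable chosen blind does not inflate the type I error.
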